3.4 Dose Modifications

All toxicity grades below are described using the NCI Common Terminology Criteria for Adverse Events (CTCAE) version 4.0.

All appropriate treatment areas should have access to a copy of the CTCAE version 4.0. A copy of the CTCAE version 4.0 can be downloaded from the CTEP website (<http://ctep.cancer.gov>).

*Please refer to the Nivolumab Investigator Brochure or [Appendix II](#) to the protocol for toxicity management algorithms which include specific treatment guidelines. These algorithms should be followed unless there are specific clinical circumstances for which the treating physician decides an alternative treatment approach is clinically appropriate. Consultation with the study chair is recommended.*

*In all of the tables for dose modification and holds in this section, the guidelines are for adverse events thought at least possibly attributed to study drug. Generally we strongly encourage early evaluation while withholding drug, and appropriate treatment as indicated in the management tables and event specific guidelines.*

Rev. 3/17

ALL OTHER EVENTS	Management/Next Dose for Nivolumab
≤ Grade 1	No change in dose
Grade 2	Hold until ≤ Grade 1 OR baseline (exceptions as noted below)
Grade 3	Off protocol therapy (exceptions as noted below)
Grade 4	Off protocol therapy
Recommended management: As clinically indicated	

- Any grade 2 drug-related uveitis or eye pain or blurred vision that does not respond to topical therapy and does not improve to Grade 1 severity within the re-treatment period OR requires systemic treatment should go off protocol treatment
- Any adverse event, laboratory abnormality, or intercurrent illness which, in the judgment of the investigator, presents a substantial clinical risk to the subject with continued study drug dosing should go off protocol treatment.
- Any grade 2-4 drug-related laboratory abnormality or electrolyte abnormality, that can be managed independently from underlying organ pathology with electrolyte replacement, hormone replacement, transfusion or insulin or that does not require treatment does not require hold/discontinuation.
- Tolerable and clinically stable grade 2 toxicities attributed to study drug may remain on study with PI approval (e.g. thrombosis that is being anticoagulated)

Rev. 12/16

Rev. 3/17

Rev. 3/17

Skin Rash and Oral Lesions	Management/Next Dose for Nivolumab
≤ Grade 1	No change in dose *

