Neurologic events	Management/Next Dose for Nivolumab
≤ Grade 1	Hold dose pending evaluation and observation. Resume with no change in dose when resolved to baseline.
Grade 2	Hold dose pending evaluation and observation. # Hold until ≤ Grade 1. Off protocol therapy if treatment with steroids is required. Resume at same dose level for peripheral isolated n. VII (Bell's palsy)
Grade 3	Off protocol therapy
Grade 4	Off protocol therapy
Patients with any CNS events including aseptic meningitis, encephalitis, symptomatic hypophysitis, or myopathy, peripheral demyelinating neuropathy, cranial neuropathy (other than peripheral n. VII), GB syndrome, myasthenia gravis should be off study.	
Recommended management: See Neurologic Adverse Event Management Algorithm	

Endocrine Hypophysitis Adrenal Insufficiency	Management/Next Dose for Nivolumab
≤ Grade 1	Asymptomatic TSH elevation * May continue therapy pending evaluation, consider endocrine consult
Grade 2	Hold until patients are on a stable replacement hormone regimen. If treated with steroids patients must be stable off steroids for two weeks. Resume at same dose level.
Grade 3	See Appendix II for diagnostic and management algorithm.
Grade 4	See Appendix II for diagnostic and management algorithm.
Note all patients with symptomatic pituitary enlargement, exclusive of hormone deficiency, but including severe headache or enlarged pituitary on MRI should be considered grade 3 events. Isolated thyroid or testosterone deficiency may be treated as grade 2 if there are no other associated deficiencies and adrenal function is monitored. Please evaluate pituitary function before beginning steroid therapy or replacement therapy of any kind. *Note patients with thyroiditis may be retreated on replacement therapy. Patients must be evaluated to rule out pituitary disease prior to initiating thyroid replacement.	
Recommended management: See Endocrine Management Algorithm	

Rev. 3/17

Renal	Management/Next Dose for Nivolumab combination
≤ Grade 1	May continue therapy per investigator discretion.
Grade 2	Hold until ≤ Grade 1. Resume at same dose level.
Grade 3	Hold until ≤ Grade 1. Resume at same dose level.
Grade 4	Off treatment

Infusion reaction	Management/Next Dose for Nivolumab combination
≤ Grade 1	May continue therapy per investigator discretion.
Grade 2	Hold until ≤ Grade 1. Resume at same dose level.
Grade 3	Hold until ≤ Grade 1. Resume at same dose level.

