Grade 4	Off treatment
Patients with fever should be evaluated as clinically appropriate. Patients may experience isolated fever during infusion reactions or up to several days after infusion. Evaluation over the course of 1-2 weeks should be done for other autoimmune events that may present as fever	

Fever	Management/Next Dose for Nivolumab combination
≤ Grade 1	Evaluate and continue at same dose level
Grade 2	Hold until ≤ Grade 1. Resume at same dose level.
Grade 3	Hold until ≤ Grade 1. Resume at same dose level.
Grade 4	Off treatment
Patients with fever should be evaluated as clinically appropriate. Patients may experience isolated fever during infusion reactions or up to several days after infusion. Evaluation over the course of 1-2 weeks should be done for other autoimmune events that may present as fever	
See Section 5 . Infusion reactions	

Rev. 3/17

Cardiac*	Management/Next Dose for BMS-936558 (Nivolumab) Cardiac Toxicities
≤ Grade 1	Hold dose pending evaluation and observation.** Evaluate for signs and symptoms of CHF, ischemia, arrhythmia or myositis. Obtain history EKG, CK (for concomitant myositis), CK-MB. Repeat troponin, CK and EKG 2-3 days. If troponin and labs normalize may resume therapy. If labs worsen or symptoms develop then treat as below. Hold pending evaluation
Grade ≥ 2 with suspected myocarditis	Hold dose.** Admit to hospital. Cardiology consult. Rule out MI and other causes of cardiac disease. Cardiac Monitoring. Cardiac Echo. Consider cardiac MRI and cardiac biopsy. Initiate high dose methylprednisolone. If no improvement within 24 hours, add either infliximab, ATG or tacrolimus. Resume therapy if there is a return to baseline and myocarditis is excluded or considered unlikely.
Grade ≥ 2 with confirmed myocarditis	Off protocol therapy. Admit to CCU (consider transfer to nearest Cardiac Transplant Unit). Treat as above. Consider high dose methylprednisolone. Add ATG or tacrolimus if no improvement. Off treatment.

* Including CHF, LV systolic dysfunction, Myocarditis, CPK, and troponin
 
** Patients with evidence of myositis without myocarditis may be treated according as "other event"
 
Note: The optimal treatment regimen for immune mediated myocarditis has not been established. Since this toxicity has caused patient deaths, an aggressive approach is recommended.
	

- Drug will be held for grade 2 cardiac dysfunction pending evaluation

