- Drug will be permanently discontinued for grade 3 or 4 cardiac dysfunction and grade 2 events that do not recover to baseline or that reoccur
- Treatment with steroids as clinically indicated

If treatment is delayed >6 weeks for an adverse event, the study PI must be consulted for any consideration of further therapy.

Patients with grade 3 thyroiditis and skin rash may continue therapy as for grade 2 events with resolution and stable replacement treatment.

Patients with thyroiditis or hypopituitarism who are stable as above may be restarted with replacement hormones including thyroid hormone and physiologic doses of corticosteroids.

Please note that grading and for hypophysitis with symptoms of headache, visual or neurologic changes or radiologic evidence of pituitary enlargement and other CNS events such as aseptic meningitis or encephalitis should be considered grade 3 events.

Any patients who require additional immune suppressive treatment beyond steroids should go off study treatment

Patients requiring > two dose delays for the same event should go off protocol therapy.

Prior to starting corticosteroids or hormone replacement for any reason, appropriate endocrine testing including cortisol, ACTH, TSH and T4 should be obtained to document baseline. However, if urgent steroid use is clinically required, steroid treatment should not be delayed for bloodwork.

Please note that in some cases the treatment algorithms recommend steroids if symptoms do not resolve in 7 days. However, this recommendation is not meant to delay steroid treatment at any time it is clinically indicated.

Patients may be dose-delayed for evaluation and restarted depending on results.

Any patient started on corticosteroids initially who is determined to not require steroid treatment for an autoimmune adverse event may resume therapy after a 2 week observation period without further symptoms at the discretion of the PI or investigator.

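### Section 3.4 gives conflicting next-dose rules for grade 2 or lower muscle inflammation without myocarditis: one line takes the patient off study, another lets dosing continue or resume.

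*Protocol*

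**What the plan says.** All of the text at issue is current wording in Protocol Section 3.4, Dose Modifications.

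**Muscle.**
- The note under the Neurologic events table names a group of conditions, muscle disease among them, and gives one outcome for all: "symptomatic hypophysitis, or myopathy, peripheral demyelinating neuropathy, cranial neuropathy (other than peripheral n. VII), GB syndrome, myasthenia gravis should be off study". It carries no grade limit.
- The double-asterisk note under the Cardiac table says "Patients with evidence of myositis without myocarditis may be treated according as" an other event.
- The only table that matches is the first one in the section, for all other events. It leaves the dose unchanged at grade 1 or lower. At grade 2 it says "Hold until ≤ Grade 1 OR baseline (exceptions as noted below". Grades 3 and 4 go off protocol therapy. One of the bullets beneath it adds "Tolerable and clinically stable grade 2 toxicities attributed to study drug may remain on study with PI approval".

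**Neurologic rows.** For an event of grade 1 or lower, the dose is held and the instruction is "Resume with no change in dose when resolved to baseline". For a grade 2 event it is "Hold until ≤ Grade 1. Off protocol therapy if treatment with steroids is required". The grade 2 row then states resumption in words only for isolated seventh-nerve (Bell's) palsy.

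**Endocrine row and general rules.** The grade 2 row of the hypophysitis and adrenal insufficiency table ends the hold once replacement hormones are stable, then adds "If treated with steroids patients must be stable off steroids for two weeks". The general rules after the tables say that stable patients with thyroiditis or hypopituitarism "may be restarted with replacement hormones including thyroid hormone and physiologic doses of corticosteroids".

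**The concern.** The two notes on muscle disease sit under different tables, and neither refers to the other. A site managing low-grade myositis without cardiac involvement can find support in Section 3.4 both for taking the patient off study and for giving the next dose. Myositis is foreseeable here: the adverse event list in Section 3.3 gives it, along with polymyositis and rhabdomyolysis, as possibly related to nivolumab.

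What is at stake is whether a patient is re-dosed after an immune-mediated event that may be serious. Time on drug and the recorded reason for stopping would also differ between sites for the same clinical picture.

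The Neurologic and endocrine rows look as if they might raise the same problem, so they are checked below as well.

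**Working it through.** No formula or planned figure is involved. The check sets the lines side by side, grade by grade.

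**1. Myositis without myocarditis, read as a myopathy**

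| Grade | Neurologic note | Cardiac note, leading to all other events | Same action? |
|---|---|---|---|
| 1 or lower | Off study | Dose unchanged | No |
| 2 | Off study | Hold, then resume; or stay on with PI approval if stable and tolerable | No |
| 3 | Off study | Off protocol therapy | Yes, treatment stops |
| 4 | Off study | Off protocol therapy | Yes, treatment stops |

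The grade 3 row of the all-other-events table allows listed exceptions, but none of them names muscle disease. The conflict is therefore confined to grade 2 and below.

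**2. Neurologic event that improves from grade 2 to grade 1**

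If rows are re-applied as the grade falls, the grade 2 row lifts the hold at grade 1 and the lower row keeps it until baseline. If each event follows the row for its worst grade, only the grade 2 row applies. The neighbouring tables settle which reading works. In the liver table, grade 1 may continue, yet grade 2 is held to normal or baseline. In the diarrhea and colitis table, grade 1 continues, yet grades 2 and 3 are held to baseline. Those baseline conditions would lapse at grade 1, and so mean nothing, if rows followed the current grade. The worst-grade reading is the coherent one, and under it the two Neurologic rows do not collide. What remains is an inverted condition: the milder event must return to baseline and the more severe one only to grade 1. In addition, resumption at grade 2 is spelled out for one condition only.

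**3. Replacement corticosteroids**

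The endocrine grade 2 row first requires a stable replacement regimen and then sets a separate condition for patients treated with steroids. The general rule counts physiologic corticosteroids among the replacement hormones on which a patient may restart. Eligibility criterion 2.1.12 likewise keeps adrenal replacement apart from systemic steroid treatment. The lines can be read together. Two gaps remain: the row does not say that its two-week condition excludes replacement, and the general rule does not name adrenal insufficiency, although that is in the table's title.

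**4. Size**

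Section 3.3 lists myositis in the column for rare but serious events, below 3%. The Schema gives an accrual goal of 70. Assuming the listed frequency carries over to this cohort, the upper figure is 0.03 × 70 = 2.1, about 2 patients. The list does not split by grade, so the number at grade 2 or lower is some part of that.

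**The case against.** The strongest reply is that the Neurologic note does not name myositis. It says myopathy, in a sentence that opens with central nervous system events, while Section 3.3 files myositis under musculoskeletal disorders. The Cardiac note is the only line in Section 3.4 that assigns myositis a next-dose rule by name, and a specific rule usually governs over a general term.

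Part of this stands. The conflict depends on treating myositis as a myopathy, which the protocol never states. But myositis is disease of muscle, the Neurologic list plainly reaches beyond the central nervous system to peripheral nerve and muscle, and neither note excludes the other or says which takes precedence. A site would have to supply that rule itself.

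A second reply is that the numbers are small, and that adverse events are recorded whether or not the next dose is given, so the toxicity table need not change. Both points are fair. The case rests on consistent re-dosing and consistent reasons for stopping, not on a distorted toxicity count.

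A third is that the Appendix II algorithm figures, and whatever the hash mark in the Neurologic grade 2 row refers to, are not visible in the text at hand and might add conditions. That cannot be checked. Even if they did, the lines of Section 3.4 would still disagree with one another. The sentence in Section 3.4 that allows clinical discretion concerns the algorithms and does not rank competing table notes.

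A reader might also infer two further contradictions: that a grade 2 neurologic event improved to grade 1 is both released and held, and that a patient on replacement corticosteroids can never resume. The documents do not support either. The first needs a current-grade reading that would empty the liver and colitis rows of meaning. The second overlooks the replacement requirement in the endocrine row itself and the express permission in the general rules.

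**Conclusion.** Section 3.4 contradicts itself on muscle inflammation without myocarditis at grade 2 or lower: off study under the Neurologic note, and continuing, or held then resumed, under the Cardiac note and the all-other-events table. Grades 3 and 4 agree. The conclusion assumes that myositis falls within the term myopathy and that off study includes stopping treatment.

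The likely reach is about 2 patients at most at full accrual, so this is a matter of safe and uniform conduct rather than a threat to the trial's efficacy result. It still merits correction, because it bears on re-dosing after a potentially serious immune event.

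The Neurologic rows (inverted restart condition, resumption stated only for Bell's palsy) and the endocrine row (no express exception for physiologic replacement, adrenal insufficiency not named in the general rule) are secondary points of wording, not contradictions.

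**What to change.** Amend Section 3.4 so that the note under the Neurologic events table, the double-asterisk note under the Cardiac table and the all-other-events table agree, with one line governing myositis or myopathy without myocarditis at each grade.

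In the same amendment:
- Align the restart wording of the Neurologic grade 1 and grade 2 rows, and state for which grade 2 events dosing may resume.
- State in the endocrine grade 2 row whether the two-week condition covers physiologic replacement, and bring the row and the general rule into line on adrenal insufficiency.

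Which rule applies in each case is for the clinical team to decide. The cost is a wording amendment: no added patients, procedures or analyses.

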The Comprehensive Adverse Events and Potential Risks list (CAEPR) provides a single list of reported and/or potential adverse events (AE) associated with an agent using a uniform presentation of events by body system. In addition to the comprehensive list, a subset, the Specific Protocol Exceptions to Expedited Reporting (SPEER), appears in a separate column and is identified with bold and italicized text. This subset of AEs (SPEER) is a list of events that are protocol specific exceptions to expedited reporting to NCI (except as noted below). Refer to the 'CTEP, NCI Guidelines: Adverse Event Reporting Requirements' [http://ctep.cancer.gov/protocolDevelopment/electronic\\_applications/docs/aeGUIDELINES.pdf](http://ctep.cancer.gov/protocolDevelopment/electronic_applications/docs/aeGUIDELINES.pdf) for further clarification. *Frequency is provided based on 2069 patients.* Below is the CAEPR for BMS-936558 (Nivolumab, MDX-1106).

**NOTE:** If an AE meets the reporting requirements of the protocol, and it is listed on the SPEER, it should **ONLY** be reported via CTEP-AERS if **the grade being reported exceeds the grade listed in the parentheses next to the event in the SPEER.**

Version 2.3, June 18, 2018

Adverse Events with Possible Relationship to BMS-936558 (Nivolumab, MDX-1106) (CTCAE 5.0 Term) [n= 2069]			Specific Protocol Exceptions to Expedited Reporting (SPEER)
Likely (>20%)	Less Likely (<=20%)	Rare but Serious (<3%)	
BLOOD AND LYMPHATIC SYSTEM DISORDERS			
	Anemia		Anemia (Gr 2)
CARDIAC DISORDERS			
		Cardiac disorders - Other (cardiomyopathy)	
		Myocarditis	
		Pericardial tamponade 	
		Pericarditis	
ENDOCRINE DISORDERS			
	Adrenal insufficiency 		
	Hypophysitis 		
	Hyperthyroidism 		
	Hypothyroidism 		
EYE DISORDERS			
		Blurred vision	
		Dry eye	
		Eye disorders - Other (diplopia) 	
		Eye disorders - Other (Graves ophthalmopathy) 	
		Eye disorders - Other (optic neuritis retrobulbar) 	
	Uveitis		
GASTROINTESTINAL DISORDERS			
	Abdominal pain		Abdominal pain (Gr 2)
	Colitis 		

Adverse Events with Possible Relationship to BMS-936558 (Nivolumab, MDX-1106) (CTCAE 5.0 Term) [n= 2069]			Specific Protocol Exceptions to Expedited Reporting (SPEER)
Likely (>20%)	Less Likely (<=20%)	Rare but Serious (<3%)	
		Colonic perforation 	
	Diarrhea		Diarrhea (Gr 3)

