	Dry mouth		Dry mouth (Gr 2)
		Gastritis	
		Mucositis oral	
	Nausea		Nausea (Gr 2)
	Pancreatitis 		
GENERAL DISORDERS AND ADMINISTRATION SITE CONDITIONS			
Fatigue			Fatigue (Gr 3)
	Fever		Fever (Gr 2)
	Injection site reaction		Injection site reaction (Gr 2)
IMMUNE SYSTEM DISORDERS			
		Allergic reaction 	
		Autoimmune disorder 	
		Cytokine release syndrome 	
		Immune system disorders - Other (GVHD in the setting of allotransplant) 	
		Immune system disorders - Other (sarcoid granuloma) 	
INJURY, POISONING AND PROCEDURAL COMPLICATIONS			
	Infusion related reaction 		
INVESTIGATIONS			
	Alanine aminotransferase increased 		Alanine aminotransferase increased (Gr 3)
	Aspartate aminotransferase increased 		Aspartate aminotransferase increased (Gr 3)
	Blood bilirubin increased 		Blood bilirubin increased (Gr 2)
	Creatinine increased		
	Lipase increased		
	Lymphocyte count decreased		Lymphocyte count decreased (Gr 2)
	Neutrophil count decreased		
	Platelet count decreased		
	Serum amylase increased		
METABOLISM AND NUTRITION DISORDERS			
	Anorexia		
		Hyperglycemia	Hyperglycemia (Gr 2)
		Metabolism and nutrition disorders - Other (diabetes mellitus with ketoacidosis) 	
MUSCULOSKELETAL AND CONNECTIVE TISSUE DISORDERS			
	Arthralgia		
		Musculoskeletal and connective tissue disorder - Other (polymyositis)	

Adverse Events with Possible Relationship to BMS-936558 (Nivolumab, MDX-1106) (CTCAE 5.0 Term) [n= 2069]			Specific Protocol Exceptions to Expedited Reporting (SPEER)
Likely (>20%)	Less Likely (<=20%)	Rare but Serious (<3%)	
		Myositis	
		Rhabdomyolysis	
NERVOUS SYSTEM DISORDERS			
		Encephalopathy 	
		Facial nerve disorder 	
		Guillain-Barre syndrome 	
		Myasthenia gravis 	
		Nervous system disorders - Other (demyelination myasthenic syndrome)	
		Nervous system disorders - Other (encephalitis) 	
		Nervous system disorders - Other (meningoencephalitis)	
		Nervous system disorders - Other (meningoradiculitis) 	
		Nervous system disorders - Other (myasthenic syndrome)	
		Peripheral motor neuropathy	
		Peripheral sensory neuropathy	
		Reversible posterior leukoencephalopathy syndrome 	

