Cytokine release syndrome may manifest as hemophagocytic lymphohistiocytosis with accompanying fever and pancytopenia.

Complications including hyperacute graft-versus-host disease (GVHD), some fatal, have occurred in patients receiving allo stem cell transplant (SCT) after receiving BMS-936558 (Nivolumab, MDX-1106). These complications may occur despite intervening therapy between receiving BMS-936558 (Nivolumab, MDX-1106) and allo-SCT.

Infusion reactions, including high-grade hypersensitivity reactions which have been observed following administration of nivolumab, may manifest as fever, chills, shakes, itching, rash, hypertension or hypotension, or difficulty breathing during and immediately after administration of nivolumab.

**Adverse events reported on BMS-936558 (Nivolumab, MDX-1106) trials, but for which there is insufficient evidence to suggest that there was a reasonable possibility that BMS-936558 (Nivolumab, MDX-1106) caused the adverse event:**

**BLOOD AND LYMPHATIC SYSTEM DISORDERS** - Leukocytosis

**CARDIAC DISORDERS** - Atrial fibrillation; Atrioventricular block complete; Heart failure; Ventricular arrhythmia

**EAR AND LABYRINTH DISORDERS** - Vestibular disorder

**EYE DISORDERS** - Eye disorders - Other (iritocyclitis); Optic nerve disorder; Periorbital edema

**GASTROINTESTINAL DISORDERS** - Constipation; Duodenal ulcer; Flatulence; Gastrointestinal disorders - Other (mouth sores); Vomiting

**GENERAL DISORDERS AND ADMINISTRATION SITE CONDITIONS** - Chills; Edema limbs; Malaise; Pain

**HEPATOBIILIARY DISORDERS** - Bile duct stenosis

**IMMUNE SYSTEM DISORDERS** - Anaphylaxis; Immune system disorders - Other (autoimmune thrombotic microangiopathy); Immune system disorders - Other (limbic encephalitis)

**INFECTIONS AND INFESTATIONS** - Bronchial infection; Lung infection; Sepsis; Upper respiratory infection

**INVESTIGATIONS** - Blood lactate dehydrogenase increased; GGT increased; Investigations - Other (protein total decreased); Lymphocyte count increased; Weight loss

**METABOLISM AND NUTRITION DISORDERS** - Dehydration; Hyperuricemia; Hypoalbuminemia; Hypocalcemia; Hyponatremia; Hypophosphatemia

**MUSCULOSKELETAL AND CONNECTIVE TISSUE DISORDERS** - Back pain;

Musculoskeletal and connective tissue disorder - Other (musculoskeletal pain); Musculoskeletal and connective tissue disorder - Other (polymyalgia rheumatica); Myalgia; Pain in extremity

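### At grade 3 the Infusion reaction table restarts nivolumab at the same dose, with no exception for hypersensitivity, which fits badly with the trial's own entry criteria

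*Protocol*

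**What the plan says.** Section 3.4 of the protocol opens with a table for all other events, whose grade 3 cell is "Off protocol therapy (exceptions as noted below"). Tables for named events follow. In the Infusion reaction table, grade 1 or lower may continue at the investigator's discretion, grades 2 and 3 share the instruction "Hold until ≤ Grade 1. Resume at same dose level", and grade 4 stops treatment. The only note under that table is about working up fever.

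Section 3.3 (the CAEPR) explains in footnote 7 what belongs to the term: "Infusion reactions, including high-grade hypersensitivity reactions which have been observed following administration of nivolumab" may present as fever, chills and rash, but also as "hypertension or hypotension, or difficulty breathing during and immediately after administration of nivolumab". The footnote is attached to the entry "Infusion related reaction". The list also carries "Allergic reaction" as a separate term under immune system disorders. Anaphylaxis appears among events whose causal link to nivolumab is not established. Neither of these two terms has a dose table in Section 3.4.

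Eligibility item 2.1.3 excludes known hypersensitivity to nivolumab or similar compounds. Item 2.1.13 excludes a history of severe hypersensitivity to any monoclonal antibody.

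**The concern.** The grade 3 row treats every infusion reaction alike. A grade 3 episode of fever and chills and a grade 3 hypersensitivity reaction with hypotension get the same instruction: wait for recovery, then give the same dose. The row contains no exception for hypersensitivity, no appeal to discretion and no precaution such as premedication.

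What is at stake is the safety of a small number of patients. A reaction that would have barred the patient from entering the trial does not, by the written rule, end treatment once the patient is on it. Whether it does depends on the investigator reaching for a general clause elsewhere.

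**Working it through.** No arithmetic decides this point; it rests on reading the sections together.

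1. **Which table applies.** The general table is labelled as covering other events, and its grade 3 cell gives way to exceptions that follow. Skin rash, diarrhea/colitis, fatigue, renal events and fever all have grade 3 rows that hold and then resume, as Infusion reaction does. These are the announced exceptions. An event classed as an infusion reaction is therefore governed by the Infusion reaction table.

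2. **Which class applies.** Footnote 7 places high-grade hypersensitivity during and just after administration within infusion reactions. Steps 1 and 2 together lead to the hold-and-resume row.

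3. **Comparison by grade.**

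| Grade | Infusion reaction table | All other events table |
|---|---|---|
| ≤ 1 | may continue, investigator's discretion | no change |
| 2 | hold, then same dose | hold until grade 1 or baseline |
| 3 | hold, then same dose | off protocol therapy |
| 4 | off treatment | off protocol therapy |

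Only grade 3 differs, so the point concerns one row of four.

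4. **Comparison with entry.** After a grade 3 hypersensitivity reaction to nivolumab, the patient has known hypersensitivity to the drug (2.1.3) and, if grade 3 is taken as severe, a severe reaction to a monoclonal antibody (2.1.13). Either would prevent registration. The dosing row allows the next infusion.

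5. **Other guidance in the document.** The grade 3 rash row leaves resumption to the investigator's discretion; the grade 3 infusion reaction row does not. Appendix II lists endocrine, gastrointestinal, hepatic, neurological, pulmonary, renal and skin algorithms, and none for infusion reactions. The Fever table sends the reader to Section 5 for infusion reactions, but Section 5 is Drug Formulation and Procurement and gives no such guidance.

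6. **What could still stop treatment.** A bullet in Section 3.4 stops treatment when the investigator judges continued dosing a substantial clinical risk. Section 3.6 stops it for unacceptable toxicity. The repeat-event rule acts only after more than two delays for the same event, that is, from the third.

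7. **Size.** The CAEPR gives frequency bands for all grades together, not grade 3 rates. Infusion related reaction is in the band of at most 20%, and allergic reaction in the band below 3%. For the accrual goal of 70: 70 × 0.20 = 14 and 70 × 0.03 = 2.1. For the cohort of 47 mentioned in Appendix V: 47 × 0.20 = 9.4 and 47 × 0.03 = 1.41. These are upper bounds for any grade. Grade 3 hypersensitivity at infusion is a subset of unknown size, so they do not estimate it.

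**The case against.** A reader might infer that Section 3.4 gives two opposite orders for the same event, resume or stop, and leaves open which prevails. The text does not support that. The general table is residual by its heading and yields to the specific tables, and footnote 7 assigns this reaction to infusion reactions. At most, a site that records the event as allergic reaction or anaphylaxis, which have no table, could arrive at the general grade 3 stop. That is a possible divergence in coding, not a contradiction in the rules.

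The strongest defence of the row as it stands is that the safeguards are real. The clinical-risk bullet covers every adverse event, Section 3.6 adds unacceptable toxicity, and Section 3.4 refers to the Investigator Brochure and recommends consulting the study chair. The brochure is not at hand and may address infusion reactions. Entry criteria also do not formally govern patients already on treatment. All of this stands and lowers the risk. It does not change the row itself, which instructs resumption and leaves the exception to be found elsewhere.

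**Conclusion.** The point holds as a gap in the grade 3 infusion reaction rule. As written, the rule resumes nivolumab at the same dose after a grade 3 hypersensitivity reaction unless a general stop is invoked, and it is out of step with eligibility items 2.1.3 and 2.1.13. It affects one grade row and, in all likelihood, few patients; the document does not allow a count.

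The conclusion rests on two assumptions: that footnote 7 is meant to define infusion reactions for dosing as well as for reporting, and that neither the Investigator Brochure nor the master protocol, which were not available, overrides the row. It is a cheap improvement for patient safety. It does not touch the trial's statistical design.

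**What to change.** Add under the Infusion reaction table in Section 3.4: *A grade 3 hypersensitivity reaction (allergic reaction or anaphylaxis) at least possibly attributed to nivolumab, including one during or immediately after infusion, is off protocol therapy. Other grade 3 infusion reactions follow the row above.* This also removes the coding divergence, since the outcome is then the same whichever term a site records. Grading stays with CTCAE version 4.0, which Section 3.4 already uses.

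In the same amendment, point the Fever table's reference for infusion reactions to this table instead of Section 5.

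The drafting cost is a short note and one cross-reference. The real cost falls on the few patients with such a reaction who might have been restarted safely: they would lose further nivolumab on this arm.
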